## **10. STATISTICAL ANALYSIS PLAN AND SAMPLE SIZE**

### **10.1 Sample Size Determination**

All trials power analyses are based on a modified intent to treat analysis, comparing the subset of intervention participants with have an actionable phenotype to the subset of control participants with an actionable phenotype. Effect sizes used to estimate power are based on prior studies of pain and depression pharmacogenetic testing and described below for each trial and shown in Table 8. Several steps were taken to generate a conservative sample size estimate. First, the power requirement was set to 90%. Second, sample sizes are adjusted for a 10% drop-out (for which UF has data from several studies that this is a good estimate). Third, slightly smaller effect sizes than what was observed in prior studies was used. Finally, sample size calculations are based on an alpha of 0.049, to allow one interim analysis with an alpha of 0.001 in each study.

Due to the study design and the delay in the control arm to obtaining the genotyping results required determine the actionable phenotype subgroup assignment, it is not feasible to directly monitor the number of randomized participants in the actionable subgroup for the enrollment stopping rule. Alternatively, the observed trial specific actionable phenotype percentages and the corresponding trial specific total enrollment targets will be used to identify when enrollment can conclude for a fully powered mITT study.

#### Acute Pain

In the University of Florida's pilot acute pain study, the difference between study arms in SIA score was -38.55 with a SD of 93.5, for a standardized effect size of 0.412. Assuming a reduced standardized effect size of 0.375, 304 participants with an actionable phenotype per group, 152 from the intervention arm and 152 from control arm, are required to achieve 90% power for a two-sided two-sample t-test. Preliminary data from the University of Florida's acute pain study indicates the proportion of participants with an actionable phenotype, genotypic or pheno-converted CYP2D6 IM or PM, will be approximately 18%. After adjusting for the subset anticipated to have an actionable phenotype, 845 participants completing all assessments, per group, are required to achieve 90% power in the sub-group analysis (1678 total). Assuming 10% drop out or lost to follow-up and 7% of participants not going on to surgery, a total of 2020 randomized participants is required to sufficiently power this study. Factoring in variability in the proportion that are IMs or PMs (15% to 24%), 1516 to 2424 randomized subjects would be need to achieve 90% power in the mITT analysis.

Chronic Pain: In the University of Florida's prior chronic pain study, the difference between study arms in composite pain score was 0.6 with a SD of 1.4, for a standardized effect size of 0.43. The same effect size was observed when assessing 3-month changes in pain scores. Assuming a standardized effect size of 0.40, 268 participants within the specified subgroup, 134 from the intervention arm and 134 from control arm, are required to achieve 90% power for a two-sided two-sample t-test. Preliminary data indicate the proportion of participants with an actionable phenotype will be 30-35%; 10-15% of participants with an actionable genotype-based phenotype (CYP2D6 IM or PM) and an additional 20% with a pheno-converted PM/IM based on drug-drug-gene interactions. After adjusting for the subset anticipated to have an actionable phenotype, 447 participants completing all assessments, per group, are required to achieve 90% power in the sub-group analysis (894 total). Assuming 10% drop out or lost to follow-up, a total of 994 randomized participants is required to sufficiently power this study. Factoring in variability of the proportion of randomized population that are IMs or PMs (24-33%), 906 to 1244 randomized subjects would be need to achieve 90% power in the mITT analysis.

#### Depression:

In prior studies of depression, the difference between study arms in PROMIS 8a T-scores was -6.7 with a SD of 10, for a standardized effect size of -.67. For the purposes of power analysis, a 4-point change is considered the minimally important difference representing a response to therapy that is congruent with the predicted CYP enzyme phenotype compared to the response to therapy which

conflicts with the phenotype.

Preliminary data from published studies indicate the proportion of participants with an actionable phenotype (CYP2C19 PM, RM, UM or CYP2D6 PM or UM, or pheno-converted CYP2D6 PM or UM) will be 40%. However, due to the distribution of study-related antidepressants in primary care and behavioral health settings, an estimated 67% of the participants with an actionable phenotype are anticipated to also have a study-related dosing or drug selection intervention. In other words, the analytic group of CYP2DC UM, PM, or CYP2C19 UM, RM, or PM phenotypes will represent a mixture of participants that may have a clinically meaningful change in depression due to being prescribed a study-relevant antidepressant and participants that may have changes in depression typical of the standard of care arm since they are not being prescribed a study-relevant antidepressant. In accounting for this population mixture, we incorporated a dilution factor of 67% into the clinically meaningful effect size projection and assume the effective difference of 0.28, representing a 2.8-point change to the T-score. We will need 542 modified intent to treat participants, 271 in each arm, to detect a standardized effect size of 0.28 with 90% power. After adjusting for the subset anticipated to have an actionable phenotype (i.e. 40%), 678 participants completing all assessments, per group, are required to achieve 90% power in the mITT analysis (1356 total). After accounting for 90% retention, 754 participants from the intervention arm and 754 participants from control arm (1508 total) are required to achieve 90% power for a two-sided two-sample t-test. Factoring in variability for the on the mITT proportion of the randomized population (40-60%), 1006-1508 randomized subjects would be needed to achieve 90% power in the mITT analysis.

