Study Population	
Acute Pain  Randomized Population  Approximately 1730* participants with planned/elective surgery who are anticipated to start a paincontrol medication with existing CPIC guidelines after their surgery
 
Analytical Population  Approximately 304 participants from the randomized population who have an actionable phenotype defined as CYP2D6 IM or PM (i.e. CYP2D6 activity score <math>\leq 0.75</math>)
 
Chronic Pain  Randomized Population  Approximately 985* participants see in primary care or pain specialty clinics who are already prescribed or anticipated to be prescribed tramadol, codeine, or hydrocodone for pain control.
 
Analytical Population  Approximately 268 participants from the randomized population who have an actionable phenotype defined as CYP2D6 IM or PM (i.e. CYP2D6 activity score <math>\leq 0.75</math>)
 
Depression  Randomized Population  Approximately 1540* participants seen in primary care or psychiatry clinics who are already prescribed or anticipate to be prescribed an SSRI with existing CPIC guidelines
 
Analytical Population  Approximately 542 participants from the randomized population who have an actionable phenotype, defined as a CYP2D6 PM or ultra-rapid metabolizer (UM), or a CYP2C19 PM, rapid metabolizer (RM), or UM

	*Subject to change based on the actionable phenotype rates and missing data.
Number of Sites	11 sites with approximately 60-80 clinics
Duration of Subject Participation:	Up to one year from consent to end of follow-up

Description of implementation of intervention (e.g.,	The intervention for ADOPT PGx is the immediate return of PGx testing results to the participant's healthcare provider.

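### Depression trial: the stated 67% dilution of a 4-point effect gives d = 0.268, not 0.28, so 271 per arm has about 87% power rather than 90%

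*Combined protocol and SAP*

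**What the plan says.** Section 10.1 (Depression) builds the effect size in three steps.

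- For the power analysis, "a 4-point change is considered the minimally important difference". The SD quoted from prior studies is 10 T-score points.
- Not every analysed participant can benefit: "an estimated 67% of the participants with an actionable phenotype are anticipated to also have a study-related dosing or drug selection intervention".
- To allow for this, the authors incorporated "a dilution factor of 67% into the clinically meaningful effect size projection and assume the effective difference of 0.28, representing a 2.8-point change".

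The sample size follows: "We will need 542 modified intent to treat participants, 271 in each arm, to detect a standardized effect size of 0.28 with 90% power". Table 9 repeats 0.28, 271 per arm and 90.00% power. On the error rate, Section 10.1 says that "sample size calculations are based on an alpha of 0.049, to allow one interim analysis with an alpha of 0.001 in each study".

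The synopsis gives slightly different randomised totals from Section 10.1 and Table 9. For depression it has "Approximately 1540* participants seen in primary care or psychiatry clinics", against 1,508. For acute pain it has "Approximately 1730* participants with planned/elective surgery", against 2,020. The asterisk marks both as subject to change with actionable rates and missing data. The acute-pain text of Section 10.1 also says that 845 completers per group "are required to achieve 90% power in the sub-group analysis (1678 total"), while Table 9 has 1,690.

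**The concern.** The 67% appears twice in the depression text, as the share of actionable participants who will have a relevant intervention and as the dilution factor. Applied to 4 points it does not give 2.8 points. The 0.28 then sets the analysed target of 542 and the 90.00% in Table 9.

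Section 10.1 sets 90% power as a requirement, describes the sample size as conservative, and ends enrolment at the total judged to give full power in the modified intent-to-treat analysis. If the effect size behind that total does not follow from its own inputs, the trial's real type II error is larger than the one it reports, and a null depression result would be read against the wrong figure.

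**Working it through.** **Inputs**

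| Input | Value | Source |
|---|---|---|
| Undiluted difference | 4 points | 10.1, Depression |
| SD | 10 points | 10.1, Depression |
| Dilution factor | 67% | 10.1, Depression |
| Alpha, test | 0.049, two-sided two-sample t-test | 10.1 and 10.4 |
| Analysed per arm | 271 | 10.1 and Table 9 |
| Actionable, retained | 40%, 90% | 10.1, Depression |

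**Method.** Power is taken from the noncentral t distribution with 2n − 2 degrees of freedom and noncentrality d × √(n/2), where n is the number per arm.

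**1. The plan's own figure.** With d = 0.28 and n = 271, the noncentrality is 0.28 × √135.5 = 3.26 and power is 90.06%. The smallest n reaching 90% is 271. The inflation also reproduces: 271/0.40 = 677.5, so 678 completers per arm; 678/0.90 = 753.3, so 754 per arm, 1,508 in total. The sample-size formula is therefore right for 0.28.

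**2. The effect size from the stated inputs.** 4 × 0.67 = 2.68 points, and 2.68/10 = 0.268. The printed 2.8 points is 2.8/4 = 70% of the undiluted effect.

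**3. Other routes to 0.28.**
- Diluting the prior-study difference of 6.7 points gives 0.67 × 6.7 = 4.5 points.
- Working back from 2.8 gives 2.8/0.67 = 4.18 points, which appears nowhere in the protocol.
- Rounding 0.268 gives 0.27, where power at 271 per arm is 87.9%.
- Reading 67% as exactly two thirds gives d = 0.2667 and power of 87.1%.

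None of these leads to 0.28.

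**4. Power at d = 0.268.**
- At 271 per arm the noncentrality is 3.12 and power is 87.4%. Type II error is 12.6%, against 9.9% at d = 0.28.
- At 1,540 randomised: 1,540 × 0.90 × 0.40 = 554 analysed, 277 per arm, power 88.1%.
- For 90% power: 296 per arm, 592 in total. From 1,540 randomised this needs 592/(1,540 × 0.90) = 42.7% actionable.

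**5. Sensitivity to the dilution factor, 271 per arm.**

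| Factor | d | Power |
|---|---|---|
| 65% | 0.260 | 85.4% |
| 66% | 0.264 | 86.4% |
| 67% | 0.268 | 87.4% |
| 68% | 0.272 | 88.3% |
| 69% | 0.276 | 89.2% |
| 70% | 0.280 | 90.1% |

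**6. The pain trials.** d = 0.375 with 152 per arm and d = 0.40 with 134 per arm each give about 90.2%, so the analysed numbers there match their stated effect sizes.

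**7. The acute-pain totals.** 152/0.18 = 844.4, so 845 per group, and 2 × 845 = 1,690. With 10% dropout and 7% not reaching surgery, 0.90 × 0.93 = 0.837; 1,690/0.837 = 2,019, which matches the printed 2,020, while 1,678/0.837 = 2,005 does not. So 1678 is a slip. For the synopsis total, with the same two loss rates, 304/(1,730 × 0.837) = 21.0% actionable. That lies inside the stated 15% to 24% range, but the rate is not printed.

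**The case against.** The strongest reply is that power is conditional on an effect size. Table 9 prints 0.28 beside 90.00%, and that pairing is correct. On this view only the explanation of how 0.28 was reached is faulty, and one clarifying sentence would do. That is a fair reading of Table 9, and it is why a justified 70% factor would be a full answer. Without one, the only derivation the protocol offers leads to 0.268, and the 90% does not belong to that value.

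The gap is also small: 0.12 T-score points, on an estimated 67% and a chosen 4-point difference. The prior-study difference of 6.7 points, diluted by 67%, would give d = 0.449 and power above 99.9%. This stands as a limit on the consequence. It does not show the trial to be badly underpowered, but the protocol chose to power on 4 points.

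A higher actionable rate could restore 90%: about 43% at 1,540 randomised is enough, near the bottom of the 40% to 60% range. That holds if enrolment stays at 1,540. The 1,006 to 1,508 range in Section 10.1 instead scales enrolment down as the rate rises, holding 271 per arm, and so leaves the gap in place.

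Finally, 271 and 277 count completers only, while Section 10.8 imputes missing values other than those due to death. At 40% actionable, 1,508 randomised includes about 603 analysable participants and 1,540 includes 616. Imputation recovers only part of the missing information, so 87% to 88% is best read as somewhat conservative.

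On acute pain, the synopsis footnote and the enrolment rule in Section 10.1 both foresee changing totals, and 1,730 is inside the printed range of 1,516 to 2,424. The 21% also depends on both loss rates: 304/1,730 is 17.6% with no losses and 304/(1,730 × 0.90) is 19.5% with dropout alone. This item is a request to state the basis and does not show lost power.

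**Conclusion.** The concern holds. On the protocol's own inputs (4 points, SD 10, 67%), the diluted effect is d = 0.268, and 271 per arm gives 87.4% power at two-sided alpha 0.049, about 2.7 percentage points below the 90.1% obtained at 0.28. At 1,540 randomised with 40% actionable and 90% retained it is 88.1%.

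These figures keep the SD at 10 in both arms. Allowing for the extra variance of a 67/33 mixture in the intervention arm lowers d to about 0.266 and power to 86.8%. The slip is confined to deriving 0.28; the calculation from 0.28 onward is sound. The 1678 and 1,730 items are minor and do not bear on this conclusion.

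**What to change.** In Section 10.1 (Depression) and the depression row of Table 9, do one of the following:

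- give the effect size as 0.268 (2.68 points) and power as about 87% for 271 per arm, adding that it is about 88% at 1,540 randomised with 40% actionable, and that 90% corresponds to 592 analysed, reached at 1,540 if about 43% are actionable; or
- keep 0.28 and 90%, and state a 70% dilution factor with its basis, bringing the 67% share of participants with an intervention into line.

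For acute pain, correct 1678 to 1,690 in Section 10.1, state the actionable and loss rates behind 1,730, and make the totals in the synopsis, Section 10.1 and Table 9 agree or cross-refer.

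The cost is a few sentences and one table row. Under the first option the reported depression power falls from 90% to about 87%. Enrolment, conduct and analysis are unchanged.

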**Table 9. Sample size calculations**

Sample size calculations for each trial, assuming an alpha of 0.049 to allow for one interim analysis

Study	Assumed Actionable Phenotype	Total N	Completed N (90% assumed)	Intervention	Usual Care	Intervention: Actionable Phenotype	Usual Care: Actionable Phenotype	Effect Size	Power
Acute Pain (CYP2D6 IM/PM)	18% (15%-24%)	2,020 (2424-1516)	1,690* (2028 - 1268)	845 (1014 - 634)	845 (1014 - 634)	152	152	0.375	90.00%
Chronic Pain (CYP2D6)	30% (24% - 33%)	994 (906 - 1244)	894 (814-1118)	447 (407-559)	447 (407-559)	134	134	0.4	90.00%
IM/PM)									
Depression (CYP2D6 or CYP2C19 PM/UM)	40% (up to 60%)	1,508 (1006)	1,356 (904)	678 (452)	678 (452)	271	271	0.28	90.00%
Total		4,522	3,940	1,970	1,970	557	557		

\*Accounts for an additional 7% of participants not completing surgery

## 10.2 General Statistical Methods

A detailed statistical analysis plan will be developed for each trial (acute pain, chronic pain, and

depression) and contained in a separate document. Prior to analysis, each trial study population details, including the number randomized, in each treatment arm, and lost to follow-up will be described. Baseline participant characteristics will be summarized as means, standard deviations, medians, and 25th, 75th percentiles for continuous variables, and as counts and percentages for categorical variables. Model assumptions will be examined prior to analysis and transformations implemented, if necessary, to more adequately meet the assumptions. Unless otherwise stated, hypotheses will be tested as two-sided with a significance level of 0.05.

### **10.3 Population for Analyses**

#### Acute pain

Participants randomized who have an actionable phenotype, specifically participants who are genotypically or pheno-converted CYP2D6 IM or PMs (i.e. CYP2D6 activity score  $\leq 0.75$ ).

#### Chronic pain

Participants randomized who have an actionable phenotype, specifically participants who are genotypically or pheno-converted CYP2D6 IM or PMs (i.e. CYP2D6 activity score  $\leq 0.75$ ).

#### Depression

Participants randomized who have an actionable phenotype, specifically participants who are genotypically or pheno-converted CYP2D6 PM or UMs or CYP2C19 PM, RM, or UMs.

### **10.4 Analysis of the Primary Endpoint**

#### Acute Pain

To determine the effect of genotype-guided drug therapy on pain control in acute pain participants, we will conduct a subset analysis comparing SIA scores at 10-days post-surgery in the Intervention group subset with CYP2D6 IM or PM phenotypes to the Control group subset with CYP2D6 IM or PM phenotypes. Participants that have other CYP2D6 phenotypes will not be included. The 10-day post-surgery SIA scores of the Intervention CYP2D6 IM/PM group will be compared to the 10-day post-surgery SIA scores of the Control CYP2D6 IM/PM group using a two-sided two-sample t-test or Mann Whitney test, as appropriate, with a type 1 error of 0.049. This primary analysis will be conducted as a modified intent-to-treat analysis, with participants analyzed and endpoints attributed according to the treatment arm to which the participants were randomized, regardless of subsequent crossover or post-randomization medical care.

#### Chronic Pain

To determine the effect of genotype-guided drug therapy on pain control in chronic pain participants, we will conduct a subset analysis comparing change in pain intensity score from baseline to 3-month follow-up in the Intervention group subset with CYP2D6 IM or PM phenotypes to the Control group subset with CYP2D6 IM or PM phenotypes. Participants that have other CYP2D6 phenotypes will not be included. The baseline to 3-month change in pain intensity of the Intervention CYP2D6 IM/PM group will be compared to the baseline to 3-month change in pain intensity of the Control CYP2D6 IM/PM group using a two-sided two-sample t-test or Mann Whitney test, as appropriate, with a type 1 error of 0.049. This primary analysis will be conducted according to modified intent-to-treat design, with participants analyzed and endpoints attributed according to the treatment arm to which the participants were randomized, regardless of subsequent crossover or post-randomization medical care.

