### 3. ENDPOINTS

#### 3.1 Primary Endpoint(s)

**Acute pain:** The primary endpoint for the acute pain study is the SIA score, a composite of pain and opioid usage, at 10 days post-surgical procedure. See Appendix A for the SIA score rationale.

**Chronic pain:** The primary endpoint for the chronic pain study is change in composite pain intensity score, assessed using the PROMIS pain intensity survey, from baseline to 3 months post return of genetic testing results to the provider.

**Depression:** The primary endpoint for the depression study is change in depression score, assessed using the PROMIS Emotional Distress - Depression 8b survey (adults) or PROMIS pediatric depressive symptoms (pediatric), from baseline to 3 months post return of genetic testing results to provider.

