#### **4.1 Randomization**

After participants provide informed consent/assent, participants will be randomized in a 1:1 allocation to the Intervention (i.e. immediate PGx testing and genotype-guided opioid or SSRI therapy with clinical decision support) and Control (i.e. usual care with delayed PGx testing) arms. Randomization will be stratified by trial and site or clinic with a random block size within each site or clinic. We anticipate variability in patient populations between recruiting sites or clinics and aim to balance the intervention assignments within the site or clinic unit. Additionally, the randomization for the chronic pain trial will be stratified by presence/absence of depression, and the randomization for the acute pain and depression trials will be stratified by pediatric/adult.

The randomization scheme will be generated by an unblinded statistician. Randomization assignments will be generated in real time in REDCap at the Coordinating Center.

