#### Depression

To determine the effect of genotype-guided drug therapy on depression symptoms in depression

participants, we will conduct a subset analysis comparing change in depression T-scores from baseline to 3-month follow-up in the Intervention group subset with either CYP2D6 PM or UM or CYP2C19 PM, RM or UM phenotypes to the Control group subset with CYP2D6 PM or UM or CYP2C19 PM, RM, or UM phenotypes. Participants that have other CYP2D6 or CYP2C19 phenotypes will not be included. Pediatric depression T-scores will be transformed to the adult scale using a published crosswalk for a combined analysis. The baseline to 3-month change in depression T-scores of the Intervention CYP2D6 PM/UM or CYP2C19 PM/RM/UM group will be compared to the baseline to 3-month change in depression T-scores of the Control CYP2D6 PM/UM or CYP2C19 PM/RM/UM subgroup using a two-sided two-sample t-test with a type 1 error of 0.049. This primary analysis will be conducted according to a modified intent-to-treat design, with participants analyzed and endpoints attributed according to the treatment arm to which the participants were randomized, regardless of subsequent crossover or post-randomization medical care.

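### Chronic pain and depression primary tests are valid and correctly sized, but omit the baseline score and the randomisation strata and so probably give up power

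*Combined protocol and SAP*

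**What the plan says.** The chronic pain endpoint in section 3.1 is the "change in composite pain intensity score, assessed using the PROMIS pain intensity survey, from baseline to 3 months" after results are returned. Section 10.4 compares the intervention subset's change with the "change in pain intensity of the Control CYP2D6 IM/PM group using a two-sided two-sample t-test or Mann Whitney test, as appropriate". For depression, section 10.4 compares change in T-score "using a two-sided two-sample t-test with a type 1 error of 0.049". Neither paragraph names a covariate or a stratum.

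The baseline scores exist: section 7.3 and Table 8 collect the pain intensity and depression surveys at baseline in these trials. Section 4.1 states: "Randomization will be stratified by trial and site or clinic with a random block size within each site or clinic". It adds that "the randomization for the chronic pain trial will be stratified by presence/absence of depression", and that the depression trial is stratified by pediatric/adult.

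Adjustment is planned, but not in the primary tests. The synopsis lists covariate adjustment among the additional analyses of each trial. Section 10.6 describes covariate-adjusted repeated-measures models, with covariates chosen because they differ between the arms.

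**The concern.** Randomisation was not carried out within the actionable subset, and section 10.6 itself warns that baseline characteristics may differ between the two actionable groups. A change score corrects for baseline with a fixed slope of one. That is usually not the best slope, so noise is left in the comparison and chance baseline imbalance is only partly removed. Leaving out the strata also means that the analysis does not match the way participants were allocated.

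The stake is precision. The plan assumes that only 30% (chronic pain) and 40% (depression) of completers enter the primary analysis, so precision from data already in hand is worth having.

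**Working it through.** **Inputs.** From section 10.1 and Table 9: two-sided alpha 0.049; chronic pain d = 0.40 with n = 134 per arm; depression d = 0.28 with n = 271 per arm. Not in the documents, so assumed: the baseline/follow-up correlation ρ (0.3, 0.5, 0.7), and the ratio s of follow-up SD to baseline SD (1 and 1.25). d is first read as standardised on the SD of change.

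**1. The plan's own figures.** Noncentral t, df = 2n − 2, noncentrality d√(n/2).
- Chronic pain: 0.40 × √67 = 3.274, power 90.2%.
- Depression: 0.28 × √135.5 = 3.259, power 90.1%.

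The smallest n reaching 90% is 134 and 271, as stated. These are sizes for unadjusted tests and take no credit for the baseline score.

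**2. Add the baseline score.** The residual variance, relative to the variance of change, is V = s²(1 − ρ²)/(1 + s² − 2ρs). With s = 1 this is (1 + ρ)/2. The noncentrality is divided by √V, with df = 2n − 3. Example, chronic pain at ρ = 0.5: 3.274/√0.75 = 3.781, power 96.4%. The denominator of V minus its numerator is (1 − ρs)², so V never exceeds 1. It equals 1 when ρs = 1. The baseline score alone therefore costs at most one degree of freedom.

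**3. Add k further terms that predict nothing.** With N = 2n, V is multiplied by (N − 1)/(N − 1 − k), and df = N − 3 − k. I take k = 11: ten site terms and one stratum term. This is an assumption. The synopsis gives "11 sites with approximately 60-80 clinics" for the three trials together, with no count per trial.

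| Trial | s | ρ | V (baseline only) | Planned | Baseline only | With 11 non-prognostic terms |
|---|---|---|---|---|---|---|
| Chronic pain | 1 | 0.3 / 0.5 / 0.7 | 0.65 / 0.75 / 0.85 | 90.2% | 98.1 / 96.4 / 94.2% | 97.7 / 95.7 / 93.3% |
| Chronic pain | 1.25 | 0.7 | 0.981 | 90.2% | 90.7% | 89.5% |
| Depression | 1 | 0.3 / 0.5 / 0.7 | 0.65 / 0.75 / 0.85 | 90.1% | 98.1 / 96.3 / 94.1% | 97.9 / 96.0 / 93.6% |
| Depression | 1.25 | 0.7 | 0.981 | 90.1% | 90.6% | 90.0% |

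**4. If the strata do predict outcome.** Suppose they explain 2, 5 or 10% of the variance of change (assumed). By the normal approximation, the strata alone raise chronic pain power from 90.4% to 91.0, 91.8 or 93.1%, and depression power from 90.2% to 90.7, 91.6 or 92.9%.

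**5. Which SD was meant.** For chronic pain, section 10.1 gives 0.6/1.4 = 0.43 and adds: "The same effect size was observed when assessing 3-month changes in pain scores". If the first figure refers to the 3-month score and the raw difference is the same on both scales, equal variances imply ρ = 0.5. That is an inference, not a stated correlation. For depression, section 10.1 says that in prior studies "the difference between study arms in PROMIS 8a T-scores was -6.7 with a SD of 10", without saying that this is the SD of change. If it is the SD at one time point, the planned test has relative variance 2(1 − ρ) and the adjusted one 1 − ρ². Planned against adjusted power is then 78.3 v 92.5%, 90.1 v 96.3% and 98.7 v 99.5% at ρ = 0.3, 0.5 and 0.7.

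**6. Validity.** In 5,000 simulated null trials per setting (chronic pain sizes), both tests rejected in 4.3 to 5.2% of runs, against a nominal 4.9%. With balanced strata explaining 10 or 20% of variance, the unadjusted test rejected in 4.0 or 2.9%: conservative, not inflated.

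**7. Interim.** At half the sample (67 and 135 per arm), the p < 0.0003 threshold of section 10.7 and s = 1, the 11-term model has 17.4/13.0/10.1% power against 8.7% in chronic pain, and 19.6/14.8/11.5% against 9.0% in depression, at ρ = 0.3/0.5/0.7. Using the same model there loses nothing under these assumptions.

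**The case against.** The strongest reply is that nothing is broken. The tests are valid, they reach the 90% target as designed, and the benefit of adjustment rests on a correlation that the documents never give. Even the direction is not guaranteed for the full model: 89.5% against 90.2%, and 90.0% against 90.1%, in the least favourable cells shown. This stands, and it makes the point a recommendation and not the correction of an error. The possible loss is small, though: 0.7 points there (90.2 − 89.5), against a gain of up to 7.5 points with the same terms in chronic pain (97.7 − 90.2).

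Three stronger readings are tempting, and the documents do not support them.
- A reader might infer that adjustment appears nowhere, or only in the repeated-measures models. The synopsis lists covariate adjustment separately from time trends, and the models of section 10.6 include baseline as a time point. What remains true is that none of this is primary.
- A reader might infer that almost all the gain comes from the baseline score and that site and stratum terms are a pure cost. That follows only from assuming that they predict nothing, whereas section 4.1 expects patient populations to vary between sites or clinics.
- A reader might put all 60 to 80 clinics into the chronic pain model and quote the loss from that many fixed terms. The count covers all three trials, so no such figure can be drawn from the documents.

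It can also be said that separate trial SAPs are announced in section 10.2 and may already adjust. They are not available here, but section 10.4 already names the tests and would need to be aligned with them. A linear model also gives up the Mann Whitney option for chronic pain; keeping the planned test as a sensitivity analysis meets that. Finally, the amendment log runs past October 2023, and the documents do not say whether the interim has taken place. The remedy therefore has to be conditional.

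**Conclusion.** The concern holds as a point about efficiency. Both primary tests omit a strong candidate covariate that is already collected, together with the factors used to balance the arms. At equal variances and ρ between 0.3 and 0.7, the baseline score alone adds 4.0 to 7.9 points of power in chronic pain (94.2 − 90.2 to 98.1 − 90.2) and 4.0 to 8.0 in depression (94.1 − 90.1 to 98.1 − 90.1). At an SD ratio of 1.25 and ρ = 0.7, only 0.5 points remain in each trial. Strata and site terms may add or cost a little, depending on how prognostic they are, which the documents do not say.

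The figures assume normal outcomes, the stated effect sizes read as those of change, and values of ρ and s that are mine. It would be wrong to conclude that the tests are biased or that the trials miss their power target because of this choice: the stated sizes reproduce. Validity here means the type I error of the tests as written and says nothing about how the actionable subset is defined.

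**What to change.** In section 10.4 and the synopsis, make the primary test of each of these two trials a prespecified linear model at two-sided alpha 0.049. The outcome stays the 3-month change; once the baseline score is a covariate, the arm effect is the same as when the 3-month score is modelled. The covariates are arm, baseline score, depression status at randomisation (chronic pain) or pediatric/adult (depression), and site. Fit site as a few fixed terms with small sites pooled, or as a random intercept for site or clinic, and state which in advance. Do not fit one fixed term per clinic. Use the same model at the interim, and leave the multiple imputation of section 10.8 in place. Keep the planned t-test or Mann Whitney test on change as a sensitivity analysis, which also covers departures from normality.

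Adopt this only if no outcome data by arm, including the interim, have been seen. If they have, keep the planned test as primary and add the model as a sensitivity analysis.

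The cost is wording; no new data are needed. If the 11 extra terms prove non-prognostic, they cost 0.4 to 0.9 points of power in chronic pain and 0.2 to 0.5 in depression at equal variances.

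Separately, and not as support for this point, three wording conflicts need reconciling:
- The synopsis analysis text compares 3-month depression scores, while the synopsis endpoint and sections 3.1 and 10.4 use change.
- The synopsis names only a t-test for chronic pain, while section 10.4 also allows Mann Whitney.
- The synopsis adjusts 6-month well-being for baseline, while section 10.5 does not.
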